Enhancing Well-Being Through Exercise During Older Age

NCT04536727

1/23/2019

“Enhancing Well-Being Through Exercise During Older Age”

Principal Investigator:

[name]
[contact]

Sponsors:

The Midwest Roybal Center for Health Promotion and Translation Pilot Grant Program

Study Locations:

The University of Illinois at Chicago
[name]

Oakwood Shores
[name]

Table of Contents

	Page
Table of Contents.....	2
A. Specific Aims.....	3
B. Background and Significance.....	3
C. Research and Design Methods.....	4
D. Protection of Human Subjects.....	11
Citations.....	14
Table 1.....	16

Research Protocol for “Enhancing Well-Being Through Exercise During Older Age”

Primary Investigator: [name]

Sponsor: The Midwest Roybal Center for Health Promotion and Translation Pilot Grant Program
Protocol Version 22

1/23/2019

A. Specific Aims

AIM 1. Determine the feasibility of adapting Fit and Strong! to include affect and mood-related content and employing this intervention among older adults with a range of depressive symptoms.

HYPOTHESIS 1. Participants will demonstrate **(1a)** adherence to the Fit & Strong! intervention defined as attendance at two-thirds or more of the exercise sessions over a 8-week period and **(1b)** acceptability of the Fit & Strong! intervention as a way to reduce depressive symptoms and improve positive affect and reduce negative affect, defined as at least 75% of participants reporting positive subjective opinions of the protocol during debriefing session assessments.

AIM 2. Begin to determine whether Fit & Strong! is efficacious as an approach for reducing depressive symptoms and improving positive affect and reducing negative affect among older adults.

HYPOTHESIS 2. Compared to wait-list participants, intervention participants will report an improvement in positive affect and a reduction in negative affect and depressive symptoms at 9 weeks as measured by medium to large effect sizes.

AIM 3. We will explore the relationship between negative/positive affect and depressive symptoms and maintenance of physical activity between groups at baseline, and 9- weeks, in order to determine whether an improvement in positive affect and a reduction in positive affect is associated with an increase in physical activity.

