HYPOTHESIS 3. Participants randomly assigned to the intervention arm will demonstrate an increase in physical activity at 9- weeks as measured by medium to large effect sizes, and this increase in positive affect/reduction in negative affect will be mediated by an increase in physical activity.

AIM 4. We will explore the relationship between physical activity and the brain between groups at baseline and 9-weeks, in order to determine whether an improvement in brain network connectivity and function is associated with an increase in physical activity.

HYPOTHESIS 4. Participants randomly assigned to the intervention arm will demonstrate an increase in physical activity and brain network connectivity and function at 9-weeks.

B. Background and Significance

Affective well-being is typically characterized as the presence of positive feelings and the absence of negative feelings over time, and have been showing to be relatively independent constructs (Lucas et al., 1996). After the age of 60, negative affect tends to remain stable, (Gross et al., 1997) but positive affect decreases (Kunzmann et al., 2000). Positive affect in late life has been positively associated with social engagement (e.g., Kunzmann, 2008), while negative affect in late life has been linked to self-reported physical health (e.g., Brief et al., 1993). Studies have demonstrated that exercise is associated with higher positive affect and lower negative affect (Dua et al., 1992; Rizk et al., 2015) In clinical samples, exercise has long been established as an

[figure not shown]

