effective treatment for depression in younger [Krogh et al., 2011] and older adults [Blake et al., 2009]. Importantly, exercise also addresses vascular risk factors thought to be particularly relevant to aging (Blaha et al., 2016), in general, as well as depression in late life [Alexopoulos et al., 2006, Sheline et al., 2010]. While there have been several studies demonstrating the benefits of exercise on depression in older adults, no known study has examined the positive benefits of a structured, group exercise program on mood and well-being in an aging sample. As an ancillary aim, we will also examine the impact of a structured exercise intervention on cognitive functioning. Fit and Strong!, a physical activity / behavior change program for older adults with lower extremity osteoarthritis, has demonstrated efficacy, effectiveness, and ease of dissemination for individuals with osteoarthritis living in the community [Hughes et al., 2004, 2006, 2010]. The goal of this study is to adapt Fit & Strong! for increasing positive affect and reducing negative affect and depressive symptoms among older adults residing in the community.

C. Research Design and Methods

C.1 General study design

We will enroll 40 subjects in this study between the ages of 60 and older, from the community who score at least 1 on the Patient Health Questionnaire-8 (PHQ). Up to 20 participants will have PHQ-8 scores of 1-4, while up to one-half of participants will have PHQ scores >4. At the outset of the study, up to 20 individuals will be randomly assigned to the intervention portion of the study, while up to 20 individuals will be randomly assigned to a crossover wait-list group, who will undergo the intervention beginning at study week 10. Outcome measures will be administered to all participants before the intervention and to the intervention group after they undergo the intervention. The wait-list group will complete all of their outcome measures before they begin the intervention(see Figure 1).

Figure 1

C.2 Phone screen and Study Visits

C2.1 Pre-Study Screen:

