Recruitment will take place at the University of Illinois at Chicago campus, Oakwood Shores, clinics, churches, parks, free online community resources including Craigslist, and surrounding community areas. Recruitment will occur through advertisements about the study to individuals through printed brochures, flyers, news papers ads and announcements about the study. This will be followed by a telephone call where potential subjects can opt to go through the telephone or in-person screening process. The Resident Service Coordinator at Oakwood Shores will aid in the distribution of recruitment material and collection of names and numbers of potential

participants. The Resident Service Coordinator will not be responsible for conducting screenings or the collection of participant data, so will not be listed as authorized research personnel.

C.5.2 Attrition and Study Non-Completers/ Issue of Dropouts:

We estimate that 33% of subjects will not complete the protocol. While it would be optimal to have higher completion rate, this rate appears to represent the nature of the population. Subjects will also be financially compensated for each visit. Subjects will receive \$55 on via check delivered through the mail.. This payment will be in the form of a check and will be mailed to the participants' desired address. The following strategies for subject retention will be used: phone reminders/confirmation of visits, and established contact with the study coordinator. We will provide participants with a document that includes a list of scheduled appointments on the back. Based on these strategies, we anticipate that drop-out will be minimized to 33% of the sample.

C.6 Assessment of Subjects

C.6.1 Screening Measures (35 minutes)

Screening Form: This questionnaire asks respondents questions about medical and psychiatric history, related to the inclusion/exclusion criteria for this study. The screening form will be utilized prior to subject enrollment, either in person or over the phone, to determine if someone would be a good fit for participation in the study. (15 minutes)

MRI Screening Form: This questionnaire asks respondents questions about their medical history and willingness to participate in the MRI testing. The MRI screening will be given either over the phone, at the time of the general study screening, or in-person during the baseline visit (5 minutes).

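### Hypotheses 2 and 3 rest on an undefined medium-to-large effect size while C 6.7 tests for significance, and at the planned size the two criteria can give opposite answers

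*Combined protocol and SAP*

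**What the plan says.** Section A, Hypothesis 2, is a between-arm statement: "Compared to wait-list participants, intervention participants will report an improvement in positive affect and a reduction in negative affect and depressive symptoms", and the yardstick is "at 9 weeks as measured by medium to large effect sizes". Hypothesis 3 predicts an "increase in physical activity at 9- weeks as measured by medium to large effect sizes" for those assigned to the intervention. That sentence names no comparator, although Aim 3 speaks of groups. Neither hypothesis gives an effect-size metric, a number for medium, a standardiser or an interval. Hypothesis 1, by contrast, sets explicit cut-offs (two-thirds attendance, 75% favourable opinions).

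C 6.7 takes another route. It plans a repeated measures ANOVA for depressive symptoms and affect, between-group analyses for significant changes, and a mixed-effects model for whether physical activity rose significantly. It states no alpha or sidedness and does not mention effect sizes or confidence intervals.

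On size, C.1 says "We will enroll 40 subjects in this study", with "up to 20 individuals will be randomly assigned to the intervention portion of the study" and "up to 20 individuals will be randomly assigned to a crossover wait-list group". C.5.2 says "we anticipate that drop-out will be minimized to 33% of the sample". There is no sample-size calculation.

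**The concern.** An effect-size label applied to a point estimate ignores sampling error. With about 13 people per arm, the standard error of a standardised difference is close in size to the threshold itself. An estimate that reaches the label may therefore be compatible with harm or with a very large benefit.

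C 6.7 adds a second, different criterion for the same outcomes and does not rank the two. The same result could then be reported as supporting Hypothesis 2 (medium effect seen) or as not supporting it (no significant change), and both reports would follow the protocol. At stake is what the pilot may claim about efficacy, and what anyone planning a later trial takes from it.

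**Working it through.** The plan states no figure to reproduce, so the check is of how the two criteria behave.

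**Inputs from the protocol.** 40 enrolled, up to 20 per arm (C.1); 33% loss (C.5.2). Completers: 40 × 0.67 = 26.8, about 13 per arm if loss is equal.

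**Assumptions not in the protocol.** Medium means d ≥ 0.5 in the favourable direction. The test is two-sided at 5%. Unless stated otherwise, d is standardised by the SD of the quantity tested (follow-up or change score).

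**Step 1: precision of an observed d of 0.5.**
- SE(d) = √(26/169 + 0.25/52) = 0.40 at 13 per arm.
- t = d√(n/2) = 0.5 × 2.550 = 1.27 on 24 df (p about 0.21); at 20 per arm, 0.5 × 3.162 = 1.58 on 38 df (p about 0.12).
- Noncentral-t 95% CI: -0.29 to 1.28 at 13 per arm; -0.13 to 1.13 at 20 per arm.

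**Step 2: where the criteria disagree.** Significance needs d ≥ t(0.975)/√(n/2).
- 13 per arm: 2.064/2.550 = 0.81.
- 20 per arm: 2.024/3.162 = 0.64.

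An observed d between 0.5 and these values meets Hypothesis 2 as worded and is non-significant.

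The band depends on the standardiser. If a change score is divided by the baseline SD, with equal SDs at both visits and baseline-to-follow-up correlation r, the needed value is multiplied by √(2(1−r)):

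| r | 13 per arm | 20 per arm |
|---|---|---|
| 0.3 | 0.96 | 0.76 |
| 0.5 | 0.81 | 0.64 |
| 0.7 | 0.63 | 0.50 |
| 0.8 | 0.51 | 0.40 |

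So at high correlation the band nearly closes at 13 per arm. At 20 per arm it closes at r = 0.7, and at 0.8 significance becomes the easier criterion.

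**Step 3: chance of reaching d ≥ 0.5 on one outcome with no true effect** (central t, 2n−2 df).
- 13 per arm: P(t > 1.27) = 10.7%. At 20 per arm: P(t > 1.58) = 6.1%.
- Change divided by baseline SD, 13 per arm, simulated: 14.5%, 10.7%, 5.8% and 2.8% at r = 0.3, 0.5, 0.7 and 0.8.
- Hypothesis 3 read as a within-arm standardised change: 4.8% (n = 13) or 1.9% (n = 20).

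**Step 4: the three outcomes of Hypothesis 2 together** (simulation, 13 per arm, no true effect).

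| Between-outcome correlation | All three pass | At least one passes |
|---|---|---|
| 0.3 | 0.8% | 26% |
| 0.5 | 1.7% | 23% |
| 0.7 | 3.3% | 20% |

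**Step 5: expected precision of the proposed estimate at 13 per arm.** Unadjusted half-width: 2.064 × √(2/13) = 0.81 SD (0.78 from the noncentral interval in Step 1). Adjusted for baseline: 2.069 × √(2/13) × √(1−r²) = 0.70, 0.58 and 0.49 SD at r = 0.5, 0.7 and 0.8.

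**The case against.** **This is a pilot, and the wording may not be a decision rule.** Aim 2 only begins to look at efficacy, and no go/no-go decision is attached. This stands as far as it goes: low power is not in itself a fault here. But a pilot's product is an estimate with its uncertainty, and the plan provides for no interval.

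**C 6.7 supplies significance tests, so a d of 0.5 at 13 per arm would not pass unchallenged.** This is right, and it means the effect-size wording cannot be called the sole criterion. It does not rescue the plan, because C 6.7 gives no alpha and does not say that its tests override Section A.

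**Stronger readings that a reader might infer.**
- That the trial has an 11% false-positive rate. The figure is per outcome and conditional on the assumptions above. Hypothesis 2 joins its three outcomes with an and. If all must pass, the chance rate is about 1 to 3%; the 20 to 26% rate applies only if any one suffices, which the protocol does not say.
- That the 11% covers Hypothesis 3. Its sentence names no comparator, and a within-arm reading gives about 5% or less.
- That a true medium effect is missed half the time because the trial is small. Any cut-off placed at the true value is missed about half the time at every sample size, so this says nothing about this design.

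**Requiring an interval that excludes zero is itself a 5% test.** Its power at true d = 0.5 is only about 23% at 13 per arm and 34% at 20. This is fair against treating such an interval as failure, so the fix calls it inconclusive.

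**Conclusion.** The point holds as a specification gap of moderate importance. Section A and C 6.7 set two criteria for the same outcomes, neither is fully defined, and neither is given precedence. With d ≥ 0.5 as medium, a two-sided 5% test and d on the scale of the test, they disagree for observed d from 0.5 to about 0.81 at 13 per arm (33% loss, equal by arm, completers only) and from 0.5 to about 0.64 if all 40 are analysed. The band's width turns on the missing standardiser, and so does the per-outcome chance rate: about 3 to 15% at 13 per arm, centred on 11%.

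The firmest part is that an estimate at the medium threshold comes with an interval reaching from below zero to beyond 1 SD, with or without the expected dropout. The documents do not support a single error rate for the trial, since they give no rule for combining outcomes.

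**What to change.** - In Hypotheses 2 and 3, replace "as measured by medium to large effect sizes" with: estimated as the baseline-adjusted between-arm difference at 9 weeks (raw, and standardised by the pooled baseline SD) with its 95% CI. This also gives Hypothesis 3 a comparator.
- In C 6.7, use the same baseline-adjusted model for the 9-week between-arm comparison in place of the repeated measures ANOVA, and apply it to physical activity too. State that this estimate and interval are the basis for each hypothesis.
- State that an interval including zero will be reported as inconclusive, neither as support for efficacy nor as evidence of no effect, and that the whole interval will inform any later trial.
- Print the expected half-width at 13 per arm: about 0.8 SD unadjusted, and about 0.70 to 0.49 SD after adjustment for baseline correlations of 0.5 to 0.8, labelled as assumed.

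The cost is a small change to the analysis model and a less favourable headline claim. No extra participants, visits or measurements are needed.

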C2.3. Exercise Intervention. Participants will be invited back to Oakwood Shores for an 8-week physical activity/behavior change intervention. The intervention will consist of the Fit and Strong! program adapted to address the impact of exercise on enhancing positive affect and reducing negative affect and depressive symptoms. Exercise classes will meet three times per week for 90 minutes per session for eight weeks. Each class is divided into 60 minutes of strength training, flexibility, and cardiovascular exercise and 30 minutes of group education/discussion, which has been adapted to include affect-oriented content. An outline of education topics for each of the 24 sessions can be found in Section C.7. Two sessions of Fit and Strong! will be delivered as part of the study; each will be limited to 20 participants. Classes will be taught by certified exercise instructors who will undergo 8-hours of training on the Fit & Strong! Program. The instructor will be trained to deliver depression specific content by a clinical psychologist Program fidelity will be monitored with the Fit and Strong! Plus Implementation Checklist and observation of the intervention by study investigators during one Fit & Strong class per 8-week session. During the intervention, participants will complete a medication adherence and group cohesion measure at baseline, 4 weeks, and 8 weeks.

C2.4. Debriefing Session: Following the intervention, a debriefing session will be held with all intervention participants. This session will be used to adapt Fit & Strong! for future study, addressing issues around affect and treatment effectiveness.

C2.5. Post-Intervention Measures. During Week 9, participants will undergo the same interview, self-report questionnaires (only those bolded in section C.6.3), mobility assessment, and

neuropsychological tests they completed during the baseline visit. Participants that were involved in the MRI testing component will also undergo the same testing for post-intervention results.

C.3 Subject Payment

All participants enrolled in the study (intervention and crossover wait list group) will be paid \$20 upon completion of their baseline interview and \$35 upon completion of their post-test. Participants will be paid in cash. Participants involved in the MRI testing will be paid \$50 in cash upon completion of the scan pre-intervention and post-intervention (\$100 total).

C.4 Entry Criteria for Studies

C.4.1 Inclusion Criteria:

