Exercise Assessment and Screening for You (Resnick, 2008) A self-report questionnaire assessing conditions that might prohibit someone from safely engaging in physical activity (2 minutes).

Six-Item Screener: (Callahan et al., 2002) A brief screen for cognitive impairment and dementia that includes three orientation items (year, month, day of the week) and delayed recall of three items. When a cut-off score of ≤ 1 error is used for diagnosing dementia, sensitivity is reported as 100.0 for community-dwelling elders. (2 minutes)

Patient Health Questionnaire (PHQ-8): A self-report questionnaire assessing symptoms of depression and appropriate for use when a clinician is not involved in the assessment.

C.6.2 Clinical Interview (Approximately 15 minutes)

World Health Organization Disability Assessment Scale (WHO-DAS-II; World Health Organization, 2000). A clinician-administered measure of functioning in six-domains (15 minutes).

C.6.3. Self-Report Questionnaires (approximately 50 minutes)

The composite list of questionnaires includes the following outcomes: health and disability status, depression and affect, physical activity, sleep and fatigue, falls, history, and balance confidence, stress and social/emotional well-being, mobility, and cognitive functioning.

Physical Activity Scale for the Elderly (PASE) [Washburn et al., 1993]. A measure of weekly physical activity (5 minutes).

Western Ontario and McMaster University Osteoarthritis Index [Bellamy et al., 1989]. Set of standardized questionnaires used to collect data on arthritis-specific symptoms using 24 parameters (5 minutes)

Self-Efficacy for Exercise Scale [Resnick and Jenkins, 2000]. A self-report questionnaire developed for older adults addressing expectations around self-efficacy regarding the ability to continue engaging in exercise in the face of hurdles to exercise (3 minutes).

Chronic Conditions: GERI-AIMS: Checklist of chronic medical conditions (3 minutes)

Cardiovascular Risk Factors Questionnaire: Adapted from the Guidelines of the American College of Sports Medicine, ACSM (2000),_A brief screening to determine subjects cardiovascular risk factors (5 minutes).

The Established Populations for the Epidemiologic Study of the Elderly (EPESE) Questionnaire: A Likert-type scale for rating of ability to complete basic and instrumental activities of daily living. (5 minutes)

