Apathy Evaluation Scale-Self Report: (Marin et al., 1991). 18-item scale asking respondents to rate symptoms of apathy on a 4-point Likert scale. (3 minutes)

Snaith-Hamilton Pleasure Scale: 14-items rated on a 4-point Likert scale reflecting experience of pleasure over the last two weeks. (3 minutes)

Activities-Specific Balance Confidence Scale (ABC; Powell et al., 1995) The ABC is a self-administered measure of balance self-efficacy. Participants indicate their level of self-confidence on a scale of 0 (no confidence)-100 (completely confident) in maintaining balance for 16 different activities performed during a typical day. Internal consistency was .96 among community-dwelling elders, with 2-week test-retest correlation coefficient of 0.92. (5 minutes)

Emotional Well Being Scale: Asks respondents to rate on a 5-point Likert scale the extent to which they experienced 6 positive emotions in the last 30 days. (2 minutes)

Life Satisfaction Survey: 5-item scale that asks respondents to list the extent to which they agree (using a 7-point Likert scale) with statements related to life satisfaction. (2 minutes)

Perceived Stress Scale: 10-items rated on a 5-point Likert scale reflecting the perception of stress in the last 30 days. (3 minutes)

The Stages of Change Questionnaire: A 4-item scale assessing physical activity. (1 minutes)

Social Provisions: A 24-item scale assessing current social behaviors. (5 minutes)

C.6.4: Mobility Measures (19 minutes)

Timed Up and Go: (Shumway et al., 2000).

Measures, in seconds, the time taken by an individual to stand up from a standard arm chair (approximate seat height of 46 cm, arm height 65 cm), walk a distance of 3 meters (approximately 10 feet), turn, walk back to the chair, and sit down (2 minutes).

Grip Strength Test: (Gershon et al., 2013): Participants are required to go through a test that assesses upper extremity strength with the use of a dynamometer (3 minutes).

Standing Balance Test: Gershon et al., 2013). This measure enables the detection of a participants' postural sway by an iPad attached to a gait belt (7 minutes).

4 Meter Walk Gait Speed Test: Gershon et al., 2013). Participants walk down an open hallway at normal pace while being timed (3 minutes).

9-Hole Pegboard Dexterity Test: (Gershon et al., 2013). Participants are asked to place pegs into a pegboard and remove them in a timely manner to assess fine motor dexterity (4 minutes).

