machine will produce imaging of each participant's brain. Participants will be allowed to request earplugs to wear during the procedure, as the machine is quite noisy. In the case that a participant should start to feel claustrophobic, the MRI testing will be stopped immediately. The total time each participant will be asked to stay inside the machine should be no more than an hour. MRI testing will take place at baseline before the exercise intervention and after the intervention (week 9). A taxi will be provided to and from the imaging center for participants that need it. Participants will be paid \$50 at each session (\$100 total).

C 6.7. Data Analysis/Interpretation: Participation rates and program acceptability ratings will be quantified. Changes in depressive symptoms and positive and negative affect will be analyzed using a repeated measures ANOVA model. Between-group analyses will be conducted to determine whether significant changes occur in the outcomes between baseline, 9- and 18-weeks to examine maintenance effects over time. A mixed-effects model will be used to determine whether intervention participants significantly increased their participation in physical activity between baseline and 9- and 18-weeks. Within-group analyses will also be conducted to determine whether participants improved in depressive symptoms, positive and negative affect, and physical activity between baseline, immediately following Fit & Strong! participation, and 2 months post-Fit & Strong! participation. Finally, the Baron and Kenny Causal Steps approach [Baron and Kenny, 1986] will be used to determine whether change in physical activity between baseline and immediately post Fit & Strong! mediates the decrease in depressive and positive and negative affect. A process evaluation will be conducted to measure aspects of program implementation including fidelity, intervention dose received, participant attrition, and program acceptability ratings. [Washburn et al., 1993; Miller et al., 1992; Bellamy, 1989; Hughes et al., 1991; Resnick and Jenkins, 2000] See Appendix C. [Maust et al., 2013; van Loon et al., 2013]

C 6.8. Data and Safety Monitoring Plan

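### Hypothesis 3 claims that activity mediates affect, but after baseline both are scheduled only once, together at week 9, so the planned test cannot tell which drives which

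*Combined protocol and SAP*

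**What the plan says.** Hypothesis 3 (section A) states that "this increase in positive affect/reduction in negative affect will be mediated by an increase in physical activity". Section C 6.7 turns this into an analysis: it uses "the Baron and Kenny Causal Steps approach" to determine "whether change in physical activity between baseline and immediately post Fit & Strong! mediates the decrease in depressive and positive and negative affect". The mediator is therefore a baseline-to-post change; no time point is given for the affect outcome.

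Aim 3 names two time points, baseline and 9 weeks. C2.5 schedules one post-intervention assessment, in week 9, at which the repeated questionnaires are completed. During the programme, C2.3 says that "participants will complete a medication adherence and group cohesion measure at baseline, 4 weeks, and 8 weeks"; neither of these measures activity or affect.

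In C.6.3 the activity scale (PASE) is described as weekly. The Emotional Well Being Scale asks for "the extent to which they experienced 6 positive emotions in the last 30 days". The pleasure scale covers two weeks. No instrument or recall window is described explicitly for negative affect.

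C 6.7 also refers to 18 weeks and to 2 months after the programme. C.1 and C.2 describe no such visit. C.1 has the wait-list begin the programme at week 10, with all its outcome measures completed before then.

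**The concern.** Mediation is a directional claim: the programme raises activity, and the rise in activity then improves affect. To support it, the design needs some point at which the activity change is seen before the affect change it is meant to explain. The visit schedule has none.

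The opposite path is credible here. C2.3 gives 30 minutes of every 90-minute class to education and discussion adapted to affect-oriented content. The programme could lift mood directly, and people who feel better may then do more.

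If that happened, the planned analysis could still report that activity mediated the benefit. C2.4 says the debriefing session will be used to adapt the programme for future study, so an unsupported mechanism could shape what comes next.

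**Working it through.** The plan gives no figure for this analysis, so there is nothing to reproduce. I made three checks.

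**1. Timing of the recall windows.** Inputs: 30 days for the Emotional Well Being Scale (C.6.3); 7 days for PASE, an assumption from the word *weekly*; week 9 taken as study days 57 to 63; windows ending the day before the visit.

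- Visit on day 60: activity window days 53–59, affect window days 30–59.
- Gap between window starts: 30 − 7 = 23 days, the same for any visit day.
- Share of the affect window before the activity window opens: 23/30 = 77%.
- For the two-week pleasure scale the gap is 14 − 7 = 7 days.
- For negative affect no gap can be calculated.

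**2. What the steps can distinguish.** Write G for arm, M for activity change and Y for affect change. The steps test (i) G on Y, (ii) G on M and (iii) M on Y given G. If M and Y swap roles, (i) and (ii) change places. Test (iii) is a test of the partial correlation of M and Y given G, which is symmetric, so its p-value is identical. Only the last step, whether the G coefficient shrinks when M is added, can differ.

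Suppose the truth is entirely affect to activity: Y = d·G + e₁ and M = r·Y + √(1 − r²)·e₂, with unit variances within arm. Then:

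- effect of G on M: r·d
- coefficient of M on Y given G: r
- apparent indirect effect: r·d × r = r²·d, a share r² of the total effect d

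That share is 9% at r = 0.3, 25% at r = 0.5 and 49% at r = 0.7, although activity mediates nothing.

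**3. Simulation of the steps.** Two-sided 0.05, with the last step taken as any shrinkage of the G coefficient. Here d is the effect on whichever variable comes first and r the slope to the other; both are assumed, since the plan says only medium to large. Arm sizes: 20 as enrolled (C.1); 13 after the 33% dropout in C.5.2 (20 × 0.67 = 13.4); 200 to see whether size helps.

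| Per arm | d, r | Verdict of activity mediating: truth activity→affect | Same verdict: truth affect→activity |
|---|---|---|---|
| 13 | 0.5, 0.5 | 3.7% | 3.2% |
| 20 | 0.5, 0.5 | 7.0% | 7.5% |
| 13 | 0.8, 0.7 | 22.3% | 22.5% |
| 20 | 0.8, 0.7 | 37.1% | 37.4% |
| 200 | 0.8, 0.7 | 100% | 100% |

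With 3,000 replicates the standard error near 37% is √(0.37 × 0.63/3000) = 0.9 points, so the differences in the rows for 13 and 20 per arm are within noise. A larger trial produces the verdict more often, whichever direction is true.

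**The case against.** **Exploratory aim in a small pilot.** Aim 3 says it will explore, and speaks of an association. That limits the consequence, but Hypothesis 3 and C 6.7 go beyond the aim.

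**The reverse case is a worst case.** The assigned programme is itself exercise, 60 minutes per class three times a week, so a path running entirely from affect to activity is an extreme. The r² shares hold only under that extreme, and the causal steps do not report a share. At medium effects the verdict is rare in either direction. These points limit how often the error would occur; they do not make a positive verdict informative about direction.

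**A stricter last step.** If the rule required the direct effect to become non-significant, pure reverse causation would leave a direct effect of d(1 − r²), for example 0.8 × 0.51 = 0.41 SD, which a large trial could detect. C 6.7 does not state such a rule, and 13 to 20 per arm would detect it unreliably. Nor would it help against a shared cause. If the programme moves both variables and a common factor links them (M = d·G + e₁, Y = r·d·G + r·e₁ + √(1 − r²)·e₂), the data have the same distribution as under true mediation.

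**The 18-week time point.** A reader might expect it to supply the ordering. No such visit is scheduled, and with the wait-list starting the programme at week 10 no untreated comparison would remain.

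**Attendance.** It is recorded before week 9 but, until week 10, only in the intervention arm, and it is not the planned mediator.

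**Conclusion.** The concern holds for direction. With one joint post-baseline assessment, a positive result from the planned steps supports an association between activity change and affect change at week 9, and no more. The symmetry of the three tests is exact; the percentages rest on assumed effects and slopes.

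Four stronger readings are tempting, and the documents do not support them:

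- **That activity and affect are measured only once.** Both also have a baseline measure and the mediator is a change score. The difficulty is that a change score over the same interval does not put the mediator before the outcome.
- **That affect as a whole is rated over a period starting three weeks before the activity period.** The 23-day gap applies to one scale of positive emotions, which the plan never names as the Hypothesis 3 outcome. It also assumes a 7-day PASE window and that this scale is among those repeated at week 9. C2.5 identifies the repeated scales by bold type, which the text I read does not preserve.
- **That Aim 3 states the reverse path.** It asks whether "an improvement in positive affect and a reduction in positive affect is associated with an increase in physical activity", which is an undirected association.
- **That Hypothesis 3 would probably be declared supported in error.** Under fully reversed causation this happened in about 3% to 37% of simulated trials at 13 to 20 per arm, depending on the assumptions.

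**What to change.** 1. In Hypothesis 3 replace *mediated by*, and in C 6.7 replace *mediates*, with *associated with at week 9*.
2. Report the reverse model (affect change as mediator, activity change as outcome) beside the planned one, from the same week-9 data. By the symmetry above it will nearly always give the same verdict, which shows the reader why no direction can be drawn.
3. State in C 6.7 that no causal direction will be concluded.
4. Reconcile the 18-week and 2-month time points in C 6.7 with the visit schedule in C.1 and C.2 and with the week-10 crossover.

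The cost is one protocol amendment and one extra model, with no new data collection. The downside is that Hypothesis 3 becomes a weaker, exploratory statement.

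I would not add week-4 measures of activity and affect with week-9 affect adjusted for week-4 affect. If activity acts on affect at the same occasion, that adjustment removes the effect already transmitted. Under true mediation of this kind, the estimated mediated share ran from about −0.60 to +0.60 depending on the assumed stability of each measure, and was zero when the stabilities were equal. It would also add a contact for the wait-list and possibly a different mode of collection in each arm. Activity would still not be randomised, so confounding of activity with affect would remain.
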